8.0 Study Endpoints

Feasibility of performing real-time electrogram morphology recurrence maps will be determined to assess if maps show specific areas of high morphology recurrence.

The acute effects of ablation will be classified as either causing AF termination, AF slowing, or no change. We will identify the number of subjects in each category.

In addition, we will collect 30 day safety endpoints that may occur after the ablation using the following Table and then categorize whether the AE/SAE is related to the procedure.

Adverse Events during or attributable to the Ablation Procedure

TYPE OF AE	Grade	Attribution categories
Adverse Event vs. SAE 
 • cardiac perforation • cardiac tamponade • Vascular • Pulmonary • Proarrhythmia • Phrenic nerve paralysis (lasting > 24 hours) • Pulmonary Vein Stenosis • GI bleed • CVA • TIA • MI • Infection • Allergic reaction during procedure • CHF • Syncope/near syncope • GI/Esophageal complications 	
Mild (grade 1): the event causes discomfort without disruption of normal daily activities.
 
Moderate (grade 2): the event causes discomfort that affects normal daily activities.
 
Severe (grade 3): the event makes the patient unable to perform normal daily activities or significantly affects his/her clinical status.
 
Life-threatening (grade 4): the patient was at risk of death at the time of the event.
 
Fatal (grade 5): the event caused death
	
Definite – The AE is clearly related to the study.
 
Probable – The AE is likely related to the study.
 
Possible – The AE may be related to the study treatment.
 
Probably unrelated- The AE is likely not related to the study
 
Unrelated – The AE is clearly NOT related to the study.

A “serious” adverse event is defined in regulatory terminology as any untoward medical occurrence that:

- **Results in death.**

If death results from (progression of) the disease, the disease should be reported as event (SAE) itself.

- **Is life-threatening.**

The patient was at risk of death at the time of the event; it does not refer to an event that hypothetically might have caused death if it were more severe.

- **Requires in-patient hospitalization or prolongation of existing hospitalization for ≥ 24 hours.**
- **Results in persistent or significant disability or incapacity.**
- **Is an important medical event**

9.0 Procedures Involved

Screening/Baseline

Assessments performed exclusively to determine eligibility for this study will be done only after obtaining informed consent. Assessments performed for clinical indications (not

exclusively to determine study eligibility) may be used for baseline values even if the studies were done before informed consent was obtained.

The screening procedures include:

- Informed Consent
- Medical history: Complete medical and surgical history
- Demographics: Age, gender, race, ethnicity
- Review subject eligibility criteria
- Review previous and concomitant medications
- Physical exam including vital signs (temperature, pulse, respirations, blood pressure), height and weight
- Pregnancy test (for females of child bearing potential).

Procedures During Treatment

Prior to Treatment

- Physical exam, vital signs
- Hematology
- Cardiac MRI or Cardiac CT Angio for left atrial and pulmonary vein anatomy
- Echocardiogram
- Left atrial thrombus will be ruled out by either transesophageal echocardiogram or Cardiac CT
- Antiarrhythmic drug therapy will be guided by the managing physician.

Ablation study

- Anesthesia – type determined by clinical factors
- Catheter insertion
- Procedural anticoagulation – intravenous heparin to maintain ACT>300 sec
- Mapping
- Ablation, as per MD operator
- Electrical cardioversion (if necessary)
- Adjunctive ablation procedure monitoring (i.e. adequacy of lesion generation, esophageal temperature monitoring, and phrenic nerve monitoring) will be employed as determined by the MD operator based on clinical needs

Follow-Up Procedures

Patients will remain on anticoagulation for a minimum of two months after the procedure. Further anticoagulation will be determined by the managing physician.

Approximately 30-90 days after ablation:

- Physical exam, vital signs
- ECG

Every 3 months:

Patients will be followed every 3-12 months, as clinically indicated, after completion of (or early withdrawal from) study treatment, for a minimum of one year.

- ECG
- Event monitoring per clinical guidelines

MRI (to be performed only if CTA is not already done)

The MRI will be performed prior to the ablation as standard of care to delineate pulmonary vein anatomy prior to the ablation procedure. The study will utilize data from this scan. This exam requires contrast-enhancement.

Subjects may receive Magnevist, Multihance, or Ablavar depending on their kidney function and the discretion of the radiology staff. Contrast will be given as follows:

- **For subjects with a GFR > 60 ml/min:**
A total dose of 0.2 mmol/kg Magnevist or Multihance or a total dose of 0.03 mmol/kg Ablavar will be injected intravenously as the contrast agent.
- **For subjects with a GFR 30-60 ml/min:**
A total dose of 0.1 mmol/kg Multihance or Magnevist or a total dose of 0.03 mmol/kg Ablavar will be injected intravenously as the contrast agent.
- **Subjects with a GFR <30 ml/min will either be excluded from this study or undergo MRI without contrast agent.**

The contrast dye will be injected intravenously at 1 ml/s, followed by 20 ml of saline flush at 1 ml/s. The scan will begin 4 seconds after first arrival of contrast in the pulmonary veins. Our researchers will utilize the data collected from the MRI to calculate atrial wall stress. Approximately 15 minutes after injection of contrast, the subjects will undergo the delayed enhancement MRI protocol. There will be an additional approximately 15 minutes of advanced sequences added to the MRI for evaluation of the atria.

The EMR/Ablation Phase

Fifteen second AF recordings will be made using a multipolar electrode catheter to map the entire right atrium and then the left atrium. Additional recordings will be made from the coronary sinus using a standard multielectrode catheter. A Lasso catheter (10 electrodes, 9 dipoles) may be used to record electrograms from the pulmonary veins, superior vena cava, and right and left atrial appendages. The 3D location of each electrogram will be documented using a commercially available 3-D mapping system (such as Carto 3, Biosense Webster, Diamond Bar, CA). Recurrence plot maps will be created using the EMR mapping software. Additional electrograms will be recorded and analyzed near sites of high recurrence based on the initial maps. We estimate an additional 20-30 minutes per atrium for the creation of the maps.

Candidate AF sources will be identified using the recurrence plot maps and maps of recurrence cycle length in conjunction with the other electroanatomic data. Radiofrequency ablation will be guided by the EMR maps. If ablation does not cause termination, the atria

will be remapped a second time to determine if another potential source still exists. If so, additional ablation will be performed at that site. After ablation based on the morphology recurrence plot, if AF has not terminated, *physician discretion will determine whether further EMR mapping guided ablation or further “standard” ablation will be performed as per physician protocol.* AF termination will be diagnosed if either sinus rhythm is restored with ablation or a regular atrial tachycardia or flutter ensues. Stable coronary sinus recordings will be used to assess ablation-induced slowing using the real-time software. The 3-D position of each ablation lesion will be documented.

10.0 **Data and Specimen Banking**

No biological specimens will be collected or stored for this research.

The data that will be stored includes demographic/clinical information on the research subject and the data from the EMR protocol. Please see section 11 for more information on the length of storage, location, access, etc. Any data requests from outside parties may also be submitted via written request to the PI and all data will be de-identified prior to release.

11.0 **Data Management**

Data Analysis

Clinical Data: Demographic and clinical data will be tabulated as means and standard deviations for continuous variables and counts with percentages for categorical variables.

For EMR Data: We will compare the cycle length prolongation seen with EMR ablation to that seen in a cohort of age and sex matched patients selected from our database of patients who have undergone a second AF ablation procedure for persistent AF with conventional methods. We will also compare acute termination rates and procedure duration. A difference of 10% in cycle length slowing between recurrence-based ablation vs. conventional ablation can be detected with 10 patients per group with 0.89 power. We will define a successful Phase I as AF termination or cycle length slowing of the coronary sinus of at least 15% in at least 7 of 10 patients from morphology recurrence mapping directed ablation.

Data Confidentiality

Stored data will include demographic/clinical information on the research subject and the data from the EMR. When possible, coded identifiers will be utilized to minimize the risk for breach of confidentiality. The PI, sub-I's, and other authorized personnel will be granted access to coded identifier lists as necessary to complete study objectives. Hard copies of paper and/or digital data will be stored in locked, limited access areas in the offices of the Cardiovascular Division, University of Miami, located on the 11th floor of the Clinical Research Building. Access to these areas is limited to authorized personnel. Electronic records will be stored in password-protected computer systems that will be accessible to authorized personnel only. Any data sent outside of the University of Miami

will be de-identified prior to release.

Record Retention

Study documentation includes all Case Report Forms, data correction forms or queries, source documents, Sponsor-Investigator correspondence, monitoring logs/letters, and regulatory documents (e.g., protocol and amendments, IRB correspondence and approval, signed patient consent forms, signed patient HIPAA authorizations). Source documents include all recordings of observations or notations of clinical activities and all reports and records necessary for the evaluation and reconstruction of the clinical research study.

Records related to this research study will be retained for the amount of time required by Federal regulations and ICH Good Clinical Practice, but no less than 6 years after the end of the study.

The PI and/or sub-I's may publish the results of this study in conjunction with appropriate scientific and medical personnel. However, data presented in published materials will not contain identifiers linking that data back to subjects. Patient name, DOB, or other elements constituting protected health information will be stripped from any data, image, etc. before publication or presentation.

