We will test this technology on ten subjects undergoing a second ablation procedure. We will map the AF utilizing the EMR to indicate locations of stable activity. This information will be provided to the cardiac electrophysiologist performing the procedure to integrate with the other electroanatomic data to develop an ablation strategy focused on ablating the drivers for AF. By targeting these drivers, we hypothesize that we can produce acute AF termination or AF cycle length prolongation. In addition to testing the real-time electrogram morphology recurrence mapping, we would also like to determine the acute effects of radiofrequency ablation of areas of high recurrence rates and determine long term freedom from AF following ablation of areas of high recurrence rates.

2.0 **Background**

Atrial fibrillation (AF) (an abnormal, rapid heart rhythm coming from the upper chambers of the heart [atria]) is the most common type of heart rhythm disorder or arrhythmia (abnormal heart rhythm). Instead of the heart beating in a steady pattern, in AF the upper chambers of the heart (atria) quiver rapidly in an unsteady manner. Atrial fibrillation may be treated with drug therapy designed to either prevent the heart rate from going too fast during atrial fibrillation (rate control therapy) or with drug therapy designed to stop the abnormal rhythm and maintain normal heart beating (rhythm control therapy). Atrial fibrillation may also be treated with catheters inserted into blood vessels that can be placed inside the heart to eliminate the critical zones or triggers for atrial fibrillation or stop those conditions that keep it going (catheter ablation). It is not known how to best locate these critical zones or triggers to be targeted by catheter ablation.

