29.0 Consent Process

Potential subjects will be identified by clinical physicians at the University of Miami and informed about the details and significance of this study. Investigators and/or study coordinators will approach the patients, explain the protocol, and ascertain whether they would be interested in participating, and prospective subjects will be provided with a copy of the approved informed consent for review. If a potential subject is interested in enrolling, informed consent and HIPAA authorization will be obtained from the subject by personnel involved in the study. Signed informed consent will be administered and HIPAA

authorization obtained either at the potential subject's clinic visit or prior to the ablation procedure.

Prospective subjects may speak languages other than English. Spanish-speaking subjects will be consented with a certified Spanish translation of the consent form. Prospective subjects who speak languages other than English or Spanish will be consented using a qualified translator to translate the English document and a translated short form of the consent in their own language.

A waiver of consent and waiver of HIPAA will be requested for matched historical control subjects. Patients in the historical control group will not undergo any research procedures; their standard of care clinical data will be used retrospectively as a comparison group to the research participants. The minimum necessary protected health information will be collected from the records of the matched historical control subjects. Only essential information will be taken from their medical records in order to ensure comparability with enrolled subjects; study team members will not contact these control subjects. The information will be stored in locked areas in the research offices of the Cardiovascular Division and password-protected computers; only personnel involved in the research will have access. Because these subjects will be historical controls and their information would be taken from medical records, it would be difficult to obtain consent and HIPAA authorizations from this group prior to reviewing their records.

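### The powered comparison with historical controls sets no equivalent cycle-length reading point, no reading method for controls, and no outcome-blind control selection.

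*Combined protocol and SAP*

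**What the plan says.** **The comparison.** Section 11.0 (Data Analysis): "We will compare the cycle length prolongation seen with EMR ablation to that seen in a cohort of age and sex matched patients". The controls come from the site's own database. A 10% difference in slowing "can be detected with 10 patients per group with 0.89 power". The SD, alpha, test and any use of pairing are not given.

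**Reading in EMR patients.** Section 9.0 (The EMR/Ablation Phase): "Stable coronary sinus recordings will be used to assess ablation-induced slowing using the real-time software". No time is attached. The same section lets the operator remap and ablate again. If AF persists after that, "physician discretion will determine whether further EMR mapping guided ablation or further" standard ablation follows.

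**Reading in controls.** Section 29.0 says only that "their standard of care clinical data will be used retrospectively as a comparison group to the research participants". It names no recording site, software or reading time. It does state comparability with enrolled subjects as an aim.

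**Selection of controls.** Sections 11.0 and 24.0 restrict controls to second ablations, by conventional technique, for persistent AF, and match them on age and sex. Section 3.0 also requires of enrolled patients that the one prior failed ablation was itself for persistent or long-standing persistent AF. The control description is silent on the indication for the first ablation.

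**The success rule.** Section 11.0 separately defines success as AF termination or coronary sinus slowing of "at least 15% in at least 7 of 10 patients from morphology recurrence mapping directed ablation". This rule uses no controls.

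**The concern.** Slowing is a change between two readings, so its meaning depends on when the second reading is taken. In an EMR patient the second reading could fall after the first EMR lesions, after remapping and further EMR lesions, or after standard lesions. In a control it is whatever the clinical record holds, plausibly an end-of-procedure value. The text permits two mismatches:

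- an EMR-step value set against a whole-procedure control value;
- an EMR value that includes the effect of standard lesions, reported as the effect of EMR ablation.

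Case mix adds to this. Controls whose first ablation had a different indication can enter the pool. They are also chosen from a database in which their acute results are already recorded, with no rule that the person choosing must not see those results.

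Any resulting difference between the groups is confounded with treatment, and a sample of 10 per group cannot reveal it. The study seeks preliminary efficacy data, so the harm would be a misleading preliminary signal in either direction.

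**Working it through.** **1. Which elements of the comparison are fixed**

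| Element | EMR group | Control group |
|---|---|---|
| Recording and method | Coronary sinus, study software (Section 9.0) | Not stated (Section 29.0) |
| Timing of data | Prospective | Retrospective |
| Post-ablation reading point | Not stated | Not stated |
| Index procedure | Second ablation, persistent AF | Second ablation, persistent AF |
| Indication for first ablation | Persistent or long-standing persistent AF (Section 3.0) | Not stated |
| Selection blind to outcome | Not applicable (enrolled before the procedure) | Not required |

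**2. The plan's own figure.** Inputs from Section 11.0: difference 10, n = 10 per group, power 0.89. Because the SD, alpha and test are missing, 0.89 cannot be reproduced. It can only be solved backwards. Assumptions: 10% means 10 percentage points of slowing, unpaired t test, two-sided alpha 0.05.

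- Noncentrality: λ = δ / (SD × √(2/n)), with 2 × 10 − 2 = 18 degrees of freedom and critical value 2.101.
- Power is the probability that a noncentral t with parameter λ exceeds 2.101 in absolute value.
- Power 0.89 requires λ = 3.371, so SD = 10 / (3.371 × √0.2) = 6.63 points.

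A one-sided test at 0.05 would imply SD 7.49. The 0.89 is attainable but cannot be verified.

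**3. Effect of a net bias with no true difference.** Let b be the systematic between-group difference in points from reading point or case mix. Then λ = b / (SD × √0.2). The values of b are illustrative; the documents give none.

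| b (points) | λ at SD 6.63 | Rejection rate, SD 6.63 | Rejection rate, SD 10 |
|---|---|---|---|
| 0 | 0 | 0.050 | 0.050 |
| 1 | 0.337 | 0.062 | 0.055 |
| 2 | 0.674 | 0.098 | 0.071 |
| 3 | 1.011 | 0.160 | 0.097 |

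At SD 10 the inflation is smaller, but power for a true 10-point difference is then only 0.56, not 0.89.

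**4. The same bias against EMR.** With a true 10-point difference and SD 6.63, the observable difference is 10 − b. Power falls from 0.89 to 0.72 at b = 2 and to 0.61 at b = 3.

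**5. Method or timing?** Percent slowing is (post − pre) / pre. If one method reads every cycle length high by a constant factor, the factor cancels. If it adds a constant, the constant cancels in the numerator and only slightly shifts the denominator. A different reading point changes the post value itself and does not cancel. The reading point is therefore the main problem and the method difference is secondary.

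**The case against.** **The wording already isolates the EMR step.** The success rule credits only ablation directed by the recurrence maps, and the Section 1.0 objective is to "determine the acute effects of radiofrequency ablation of areas of high recurrence rates". A reader might infer from Section 8.0 ("The acute effects of ablation will be classified as either causing AF termination, AF slowing, or no change") that slowing from standard lesions may count towards 7 of 10. The documents do not support that: Section 8.0 reports on the Section 1.0 objective, and the rule's own wording excludes such lesions. This part of the objection stands. What the rule lacks is a time stamp that makes its wording operational. Intent in the EMR arm also says nothing about when controls are read.

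**Controls are not chosen on age and sex alone.** A reader might infer that they are. In fact they must also be second ablations for persistent AF from the same site, which mirrors most of the main eligibility criterion. That stands too. The remaining gap is the indication for the first ablation, where the short description may be shorthand, and the absence of outcome-blind selection. Section 29.0 aims at comparability but names no variable or procedure to secure it.

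**Different instruments need not bias the result.** This is largely right for a stable offset, as shown above.

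**The illustration is generic.** Also fair. The bias values are chosen and the SD is back-solved. The figures show how sensitive a 10-per-group comparison is, not how large the bias will be.

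**It is a feasibility study.** The historical comparison is not among the Section 8.0 endpoints and does not drive the success decision. That lowers the severity. It does not remove the point, because the protocol attaches a power figure to this comparison.

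**Conclusion.** The concern holds in limited form. The only powered comparison has no stated reading method for controls and no post-ablation reading point for either group. Its control pool also omits one enrolment criterion and any requirement to select without sight of outcome. The plan can be followed exactly and still compare non-equivalent readings.

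The size and direction of any bias are unknown. Under the assumptions in the working (two-sided unpaired t test, alpha 0.05, implied SD 6.6 points), a 2- or 3-point bias would raise the false-positive rate from 5% to about 10% or 16%.

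Two stronger conclusions should not be drawn. The 7-of-10 rule is not broken: it does not use controls and already limits credit to EMR-directed ablation. Nor do the documents show that any bias has occurred or favours EMR. This is a cheap improvement of low to moderate severity.

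**What to change.** Amend Section 11.0. These are measurement and selection rules only; the ablation does not change.

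- **(a) EMR-step reading.** State that EMR-step slowing, including for the 7-of-10 rule, is read at the end of EMR-guided ablation and before any standard ablation. This makes the rule's existing wording operational.
- **(b) Control comparison.** Read both groups at one equivalent point, such as the last AF recording before termination, cardioversion or end of ablation, by the same method where control recordings exist. This compares whole procedures, including any standard lesions, so report the EMR-step value alongside. If it cannot be done, label the comparison descriptive and remove the 0.89 power claim.
- **(c) Controls.** Apply the Section 3.0 prior-ablation criterion to controls and select them without sight of outcome. For the cycle-length analysis, require a readable baseline AF cycle length in both groups. A requirement on controls alone would create a new asymmetry.
- **(d) Reporting.** Give baseline coronary sinus cycle length by group.

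**Cost.** An amendment with IRB approval (Section 12.3), re-reading about 20 recordings (10 per group) if control recordings exist, which the protocol does not say, and a smaller control pool.
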